10. EXPERIMENTAL PLAN

10.1 OVERVIEW

This study will be conducted in accordance with U.S. Code of Federal Regulations, the Declaration of Helsinki, ISO 14155 and all other applicable laws and regulations. The study will not begin until IRB approvals have been obtained.

This study will be a post-market, prospective, multicenter, bilateral, randomized, open-label, cross-over, comparative clinical study conducted at up to 7 sites in the U.S. Approximately 140 subjects will be randomized and bilaterally implanted, resulting in approximately 110 evaluable subjects (55 in the study arm and 55 in the control arm).

After signing the informed consent, subjects meeting all inclusion and exclusion criteria will be randomized to either the Study group or the Control group.

The duration of study participation is from the initial Preoperative Visit #1 to a final visit at 3 months or 4 months after the second-eye cataract surgery, depending upon the subject's randomized group assignment. All subjects in both arms are intended to have bilateral cataract surgery. The subjects randomized to Study group will undergo preoperative LipiFlow treatment and the subjects randomized to Control group will not receive preoperative LipiFlow treatment. Three months postoperatively, both groups will be evaluated for clinical outcomes and the Control group will receive LipiFlow treatment as the cross-over group. The Control group will be evaluated at 4 months postoperative for clinical outcomes.

Key data collection for all subjects/eyes includes distance visual acuities, manifest refraction, contrast acuity, keratometry, biometry, corneal topography, visual symptoms, Meibomian gland evaluation, biomicroscopic slit-lamp findings, complications and adverse events. A chart summary of all examination or treatment procedures required at each study visit is provided in **Appendix B**. If needed, specific equipment necessary to perform the required procedures will be supplied for the duration of the study (**Appendix C**). The study visit schedule is described in Section 10.2.

Although the study is not masked, to maintain consistency, it is recommended that a single individual (study technician or coordinator designated by the investigator) conduct all study-related vision testing, although a back-up person should also be designated and trained.

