10.2 VISIT SCHEDULE

The study visit schedule for all study subjects is outlined in **Table 1**.

Subjects randomized to the **Study Group** will undergo a minimum of the following four study visits (with visit windows shown in parentheses):

- 1) Preoperative Visit #1, including LipiFlow treatment (may occur on the same day or within 1 week of Visit #1)
- 2) Preoperative Visit #2 (2 - 4 weeks after LipiFlow treatment)
- 3) 1 Month Postop (30 - 60 days after cataract surgery on second eye)
- 4) 3 Months Postop (10 to 14 weeks after cataract surgery on second eye)

Subjects randomized to the **Control group** will undergo a minimum of the following five study visits (with visit windows shown in parentheses):

- 1) Preoperative Visit #1
- 2) Preoperative Visit #2 (2 - 4 weeks after Preoperative Visit #1)
- 3) 1 Month Postop (30-60 days after cataract surgery on second eye)
- 4) 3 Months Postop (10 to 14 weeks after cataract surgery on second eye), including the crossover LipiFlow treatment, which should occur within 0 - 7 days after the 3 months postoperative visit
- 5) 4 Months Postop (4 to 6 weeks after receiving crossover LipiFlow treatment)

Unscheduled visits may be conducted as necessary at the discretion of the investigator for medically-indicated follow-up.

Table 1: Visit Schedule

NAME OF VISIT	GROUPS	PROCEDURES	VISIT WINDOW
Preoperative #1	All	Informed Consent, Screening, Baseline, Randomization and Enrollment	Per site practice
LipiFlow Treatment	Study Group	LipiFlow treatment	LipiFlow treatment can occur on the same day or within 1 week of Visit #1
Preoperative #2	All	Preoperative	Study Group: 2-4 weeks after LipiFlow treatment; Control Group: 2-4 weeks after Visit #1
1 Month Postop	All	1 month postoperative	30-60 days after cataract surgery on second eye
3 Months Postop	All	3 months postoperative; The crossover Control group will receive LipiFlow treatment within 0-7 days after the 3 months postoperative visit	10 to 14 weeks after cataract surgery on second eye
4 Months Postop	Crossover Control Group Only	4 months postoperative	4 to 6 weeks after receiving crossover LipiFlow treatment

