- Mean MRSE at 4 months postoperative will be compared to target MRSE.
- Frequency and percent of eyes with MRSE within 0.50 D and within 1.00 D of target MRSE at 4 months postoperative will be reported.
- Mean change in total meibomian gland score and mean change in total SPEED score from 3 months to 4 months postoperative will be reported. An increase in both total Meibomian gland score and total SPEED are expected.
- The frequency and proportion of eyes with optical/visual, medical and lens complications will also be reported over time. Rate of adverse events will be reported in the Study and Control groups.

[figure not shown]

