#### 4.2.4 RATE OF ADVERSE EVENTS/MEDICAL AND/OR LENS FINDINGS

The frequency and proportion of eyes with optical/visual, medical and lens complications will be reported over time. The type and rates of adverse events will be summarized for both study group eyes and control group eyes.

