Mean monocular BCDVA - (N, Mean, SD, Min, Max, 95% Cl of LogMAR)  Monocular BCDVA by acuity line over time (n and % within each category)	х	eyes
Mean binocular UCDVA, UCIVA, UCNVA, BCDVA - (N, Mean, SD, Min, Max, 95% CI of LogMAR) Binocular UCDVA, UCIVA, UCNVA, BCDVA by acuity line over time (n and % within each category)	х	Subjects
MRSE at 3M - (N, Mean, SD, Min, Max, 95% CI)  Difference between 3M MRSE and target MRSE - (N, Mean, SD, Min, Max, 95% CI)	х	eyes
Contrast acuity at 3M - (N, Mean, SD, Min, Max, 95% CI of LogMAR)	х	Subjects
Mean change in SPEED score from baseline- (N, Mean, SD, Min, Max, 95% CI)	х	eyes
Mean change in total Meibomian gland score from baseline- (N, Mean, SD, Min, Max, 95% CI)	х	eyes

ENDPOINTS EVALUATED at 4-MONTH POSTOP		
Mean monocular BCDVA and UCDVA and change from 3M to 4M - (N, Mean, SD, Min, Max, 95% Cl of LogMAR)	х	Control group eyes only
Monocular BCDVA and UCDVA by acuity line over time (n and % within each category)		
Mean binocular UCDVA, UCIVA, UCNVA, BCDVA and change from 3M to 4M - (N, Mean, SD, Min, Max, 95% CI of LogMAR) Binocular UCDVA, UCIVA, UCNVA, BCDVA by acuity line over time (n and % within each category)	х	Control group subjects only
MRSE at 4M - (N, Mean, SD, Min, Max, 95% CI)  Difference between 4M MRSE and target MRSE - (N, Mean, SD, Min, Max, 95% CI)	х	Control group eyes only
Contrast acuity at 4M and change from 3M to 4M - (N, Mean, SD, Min, Max, 95% CI of LogMAR)	х	Control group subjects only
Mean change in SPEED score from baseline- (N, Mean, SD, Min, Max, 95% CI)	х	Control group eyes only
Mean change in total Meibomian gland score from baseline- (N, Mean, SD, Min, Max, 95% CI)	х	Control group eyes only
RATE OF ADVERSE EVENTS/MEDICAL/LENS FINDINGS		
Type and rate of AE, medical and/or lens findings (n and %)	х	eyes

**KEY**: MGYLS=Meibomian gland yielding liquid secretion, TBUT=tear break-up time, SPEED=standard patient evaluation of eye dryness, MGD=Meibomian gland dysfunction, AC=axial length, ACD=anterior chamber depth, K=keratometric measurements, UCIVA=uncorrected intermediate VA at 66cm, UCNVA=uncorrected near VA at 40cm, UCDVA=uncorrected distance visual acuity, BCDVA=best-corrected distance visual acuity

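### Adverse event rates are summarised by randomized arm with no cut-off at the crossover, so the Control rate mixes untreated time with post-LipiFlow time and longer follow-up

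*SAP*

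**What the plan says.** **Reporting of adverse events.** SAP 4.2.4 has two sentences. The first concerns complications and has a time element: "The frequency and proportion of eyes with optical/visual, medical and lens complications will be reported over time". The second concerns adverse events and has none: "The type and rates of adverse events will be summarized for both study group eyes and control group eyes". Appendix I gives one line, beginning "Type and rate of AE, medical and/or lens findings (n and", shown by Study and Control group and counted in eyes. Protocol 20.3 is to the same effect: "Rate of adverse events will be reported in the Study and Control groups".

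**Length of follow-up.** Protocol 10.1 makes the end of participation depend on the arm: a "final visit at 3 months or 4 months after the second-eye cataract surgery". The windows are in Protocol 10.2:

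- Both arms: "3 Months Postop (10 to 14 weeks after cataract surgery on second eye".
- Crossover LipiFlow in Control, "which should occur within 0 - 7 days after the 3 months postoperative visit".
- Control only: "4 Months Postop (4 to 6 weeks after receiving crossover LipiFlow treatment".

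Protocol 10.6 asks for adverse events to be assessed at every visit, and Protocol Appendix B marks them at month 4.

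**Efficacy is handled differently.** SAP 4.2.2 makes the between-arm comparisons at 3 months. SAP 4.2.3 takes the 4-month data for Control alone, and the 4-month rows of Appendix I are labelled accordingly. The adverse event row has no such label.

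**The concern.** A reader of the safety table will take the two columns as preoperative LipiFlow against no LipiFlow. That holds only up to the crossover. After it, Control eyes have had the same treatment and go on accruing events, while Study eyes have left the trial.

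Protocol 17 lists short-lived events that LipiFlow may cause, among them eyelid and ocular surface irritation or inflammation. Over full follow-up these enter both columns, so an excess caused by the treatment tends to cancel. The extra Control time then adds background events to one side only. Both effects make preoperative LipiFlow look safer than it would in a summary that stops at month 3.

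**Working it through.** The documents state no adverse event rate, so there is no figure of the plan's own to reproduce. The follow-up times come from the visit windows. The effect on the rates needs assumptions, which are marked.

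**Step 1. Extra follow-up in Control (Protocol 10.2).**

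- From the 3-month visit: minimum 0 + 4 = 4 weeks; maximum 1 + 6 = 7 weeks.
- From second-eye surgery: Study 10–14 weeks; Control 10 + 4 = 14 to 14 + 7 = 21 weeks.
- With the 3-month visit at 12 weeks, the ratio of Control to Study postoperative time is 16/12 = 1.33 to 19/12 = 1.58.
- Study's second preoperative visit is timed from LipiFlow, which may fall up to 1 week after Visit #1. Study's preoperative phase can therefore be up to 1 week longer, and the net difference over the whole study is 4 − 1 = 3 to 7 − 0 = 7 weeks.

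**Step 2. Effect of longer follow-up alone (assumed: 10% event rate in Study, equal constant hazard from Visit #1).** At mid-window, with no gap between the second preoperative visit and second-eye surgery, Study has 0.5 + 3 + 12 = 15.5 weeks and Control 3 + 12 + 0.5 + 5 = 20.5 weeks. An assumed 4-week gap makes these 19.5 and 24.5.

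- No gap: 1 − 0.90^(20.5/15.5) = 13.0% in Control.
- 4-week gap: 1 − 0.90^(24.5/19.5) = 12.4% in Control.

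Some gap must exist, because both eyes are operated on after that visit. On 110 eyes per arm (55 subjects × 2), the excess of 2.4–3.0 points is about 3 eyes.

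**Step 3. Adding the LipiFlow events.** Let p be the background risk per eye over 12 postoperative weeks, q the risk from one LipiFlow treatment (assumed equal in both arms), and e the extra weeks in Control (4 or 7). The background hazard is assumed constant.

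- Study: 1 − (1 − p)(1 − q)
- Control to month 3: p
- Control over full follow-up: 1 − (1 − p)^((12 + e)/12) × (1 − q)

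| p | q | Study | Control to month 3 | Difference to month 3 | Control, full (e = 4; 7) | Difference, full (e = 4; 7) |
|---|---|---|---|---|---|---|
| 2% | 1% | 2.98% | 2.00% | +0.98 | 3.63%; 4.12% | −0.65; −1.14 |
| 2% | 5% | 6.90% | 2.00% | +4.90 | 7.52%; 7.99% | −0.62; −1.09 |
| 5% | 3% | 7.85% | 5.00% | +2.85 | 9.41%; 10.57% | −1.56; −2.72 |
| 10% | 1% | 10.90% | 10.00% | +0.90 | 13.97%; 16.21% | −3.07; −5.31 |
| 10% | 5% | 14.50% | 10.00% | +4.50 | 17.45%; 19.60% | −2.95; −5.10 |

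Differences are Study minus Control in percentage points. To month 3 the difference is q(1 − p), the quantity of interest. Over full follow-up it is −(1 − q)(1 − p)[1 − (1 − p)^(e/12)], which cannot be positive. The reversal is thus built into the assumptions of equal q and a continuing background hazard. If no background event occurred after month 3, the difference would be zero: hidden rather than reversed.

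**The case against.** **The output is descriptive.** This stands. The SAP summarises adverse events, with no test, success criterion or expected direction, and they are not a key endpoint. A reader might infer that a formal safety comparison is biased; none is planned.

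**The pooling is inferred from silence.** Also true. No sentence says that post-crossover events belong in the Control rate. The Appendix I row is weak evidence by itself, because it also shows no time split for the medical and lens findings that the text does report by time. But no rule keeps those events out, and the plan separates the crossover period for efficacy and not for adverse events.

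**Other safety information is unaffected.** A reader might infer that this is the trial's only safety contrast, or that LipiFlow events are charged to Control alone. Neither is supported. Complications are reported over time, staining at 1 month and symptoms at 3 months are summarised by arm before crossover, and the Study column carries its own LipiFlow events.

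**Device-related events can be identified.** Protocol 11.4 has investigators grade causality, and 11.3 sends device-related events to a dedicated form. The data may therefore allow a separation, but the SAP plans no table that uses them.

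**A by-visit table would be enough.** Not reliably. Protocol 11.3 records an event on the form for the visit at which the site became aware of it. Crossover treatment may be given on the day of the 3-month visit, and Protocol Appendix B puts both in one column, with a slit-lamp exam before and after treatment. A same-day LipiFlow event could appear as a 3-month Control event.

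**The magnitude is fragile.** This stands. Several listed events, such as toxic anterior segment syndrome, occur early after surgery. A front-loaded hazard shrinks the part due to longer follow-up, but not the part due to crossover LipiFlow.

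**Conclusion.** The point holds as a gap in safety reporting that should be closed. Followed as written, the descriptive Control rate covers untreated time, one LipiFlow treatment and 4 to 7 weeks beyond the 3-month visit (about 3 to 7 weeks net). It cannot then be read as the rate without LipiFlow.

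The follow-up difference comes directly from the visit windows. The direction of the distortion needs only that crossover LipiFlow causes some events, or that some background events occur after month 3. Its size depends on rates the documents do not give. The 12.4–13.0% and the ranges of +0.9 to +4.9 and −0.6 to −5.3 points are illustrations under assumed rates, constant hazard and, for the ranges, equal LipiFlow risk in both arms. They are not estimates for this trial. The visual acuity success criterion and the sample size are untouched.

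**What to change.** In SAP 4.2.4 and the Appendix I row, replace the single summary by two:

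- (a) Adverse events by randomized arm, from randomization to the 3-month visit and before any crossover treatment. This is the between-arm summary.
- (b) Control only: adverse events from crossover LipiFlow to the 4-month visit, reported separately.

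Confirm that the case report form records whether onset was before or after crossover treatment. The protocol describes recording by visit of awareness and mentions no onset-date field, so this should not be taken for granted; same-day events depend on it.

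A comparison of the arms over equal windows after LipiFlow is tempting but should not be added. Study subjects return 2–4 weeks after treatment and then have cataract surgery, so a 4–6-week window can include surgical events, while the Control window falls after the 3-month visit. That contrast would be confounded by surgery.

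The cost is revised SAP wording, slightly more table work and possibly one check of the form.

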#### 5 SAMPLE SIZE CALCULATIONS

The sample size determination is based on the primary endpoint of uncorrected distance visual acuity (UCDVA). There is over 90% power to detect a 1-line or greater difference in mean UCDVA between the treatment and control groups with 55 subjects in each group. This assumes one-sided two-sample t-test with an alpha of 0.05 and standard deviation of 1.6 lines. Adding 20% screen failure/drop-out rate will require enrolling 69 subjects per group.

#### 6 STUDY INTERIM REPORTS

An interim database lock will be performed for preoperative data after completion of the second preoperative visit.

Version 1.0 6 SAP/DRYE-102-SELF

#### **APPENDIX I: TABLE LISTING**

Variable	All Subjects	Study/control group	Note
ENROLLMENT/PREOP/OP			
Accountability/Enrollment			
Subjects/eyes by investigational site (n)	x	X	Subjects and eyes
Accountability table over time – (Available for analysis, Missing data –Forms not yet completed, Active, Missed visit, Lost to follow-up, Discontinued) (n and %)	Х	х	Subjects and eyes
Out of Interval listing	Х	Х	Subjects and eyes
Demographics			
Demographic – Age in years (N, Mean, SD, Min, Max), race, sex, ethnicity (n and %) Age in groups (<30, 30-39, 40-49, 50-59, 60-69, ≥70) (n, %)	х	х	Subjects
Preoperative Characteristics			
Target refraction (MRSE) - (N, Mean, SD, Min, Max)		x	eyes
BSCVA in groups (≤20/30, 20/40, 20/50-20/80, 20/100, >20/100) – (n,%)		х	eyes
Total Meibomian gland score at 1 st preop visit (baseline)- (N, Mean, SD, Min, Max, 95% CI)		х	eyes
Number of MGYLS at 1 st preop visit (baseline) – (N, Mean, SD, Min, Max, 95% CI)		x	eyes
TBUT at 1 st preop visit (baseline) – (N, Mean, SD, Min, Max, 95% CI)		x	eyes
SPEED score at 1 st preop visit (baseline) – (N, Mean, SD, Min, Max, 95% CI)		x	eyes
Eyelid margin evaluation assessment (obvious/minimal changes/normal appearance; Obvious/Non-obvious MGD) at 1st preop visit (baseline) – (n, %)		х	eyes
KEY STUDY ENDPOINTS			
Mean monocular UCDVA at 3-month (N, Mean, SD, Min, Max, 95% CI of LogMAR)		х	Eyes, also by right eye and left eye

Precision (avg. of SD from 3 sets of measurements) of preop (2 nd visit) AL, ACD and Ks	x	Eyes, also by right eye and left eye
Rate of MRSE predictability at 3-month (achieved MRSE within 0.5D/1.0D of target MRSE) – (n, %)	х	Eyes, also by right eye and left eye
Rate of bothersome ocular symptoms at 3-month – (n, %)	х	subjects
Mean change in total Meibomian gland score from baseline to 1- month – (N, Mean, SD, Min, Max, 95% CI)	х	Eyes, also by right eye and left eye
ENDPOINTS EVALUTED AT 1-MONTH POSTOP		
Mean change in number of MGYLS from baseline – (N, Mean, SD, Min, Max, 95% CI)	х	eyes
Mean change in ocular surface stain grade from baseline— (N, Mean, SD, Min, Max, 95% CI)	х	eyes
Mean change in TBUT from baseline- (N, Mean, SD, Min, Max, 95% CI)	х	eyes
Eyelid margin evaluation assessment (obvious/minimal changes/normal appearance; Obvious/Non-obvious MGD) at 1-month – (n, %)	х	eyes
ENDPOINTS EVALUTED AT 3-MONTH POSTOP		
Mean monocular BCDVA - (N, Mean, SD, Min, Max, 95% Cl of LogMAR)  Monocular BCDVA by acuity line over time (n and % within each category)	х	eyes
Mean binocular UCDVA, UCIVA, UCNVA, BCDVA - (N, Mean, SD, Min, Max, 95% CI of LogMAR) Binocular UCDVA, UCIVA, UCNVA, BCDVA by acuity line over time (n and % within each category)	х	Subjects
MRSE at 3M - (N, Mean, SD, Min, Max, 95% CI)  Difference between 3M MRSE and target MRSE - (N, Mean, SD, Min, Max, 95% CI)	х	eyes
Contrast acuity at 3M - (N, Mean, SD, Min, Max, 95% CI of LogMAR)	х	Subjects
Mean change in SPEED score from baseline- (N, Mean, SD, Min, Max, 95% CI)	х	eyes
Mean change in total Meibomian gland score from baseline- (N, Mean, SD, Min, Max, 95% CI)	х	eyes

ENDPOINTS EVALUATED at 4-MONTH POSTOP		
Mean monocular BCDVA and UCDVA and change from 3M to 4M - (N, Mean, SD, Min, Max, 95% Cl of LogMAR)	х	Control group eyes only
Monocular BCDVA and UCDVA by acuity line over time (n and % within each category)		
Mean binocular UCDVA, UCIVA, UCNVA, BCDVA and change from 3M to 4M - (N, Mean, SD, Min, Max, 95% CI of LogMAR) Binocular UCDVA, UCIVA, UCNVA, BCDVA by acuity line over time (n and % within each category)	х	Control group subjects only
MRSE at 4M - (N, Mean, SD, Min, Max, 95% CI)  Difference between 4M MRSE and target MRSE - (N, Mean, SD, Min, Max, 95% CI)	х	Control group eyes only
Contrast acuity at 4M and change from 3M to 4M - (N, Mean, SD, Min, Max, 95% CI of LogMAR)	х	Control group subjects only
Mean change in SPEED score from baseline- (N, Mean, SD, Min, Max, 95% CI)	х	Control group eyes only
Mean change in total Meibomian gland score from baseline- (N, Mean, SD, Min, Max, 95% CI)	х	Control group eyes only
RATE OF ADVERSE EVENTS/MEDICAL/LENS FINDINGS		
Type and rate of AE, medical and/or lens findings (n and %)	х	eyes

**KEY**: MGYLS=Meibomian gland yielding liquid secretion, TBUT=tear break-up time, SPEED=standard patient evaluation of eye dryness, MGD=Meibomian gland dysfunction, AC=axial length, ACD=anterior chamber depth, K=keratometric measurements, UCIVA=uncorrected intermediate VA at 66cm, UCNVA=uncorrected near VA at 40cm, UCDVA=uncorrected distance visual acuity, BCDVA=best-corrected distance visual acuity

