- Change in Eyelid Margin Evaluation from Baseline visit to 1 month postoperative in the Study group compared to the Control group.

The eyelid appearance will be graded as 'Obvious lid changes', 'Minimal lid changes' or 'Normal lid changes'. In addition, the eyelids for the presence of MGD will be graded as either 'Obvious MGD' or 'Non-obvious MGD'. The frequency and percent of eyelid assessment and MGD presence assessment will be presented at Baseline visit and 1 month postoperatively.

- **3-Month Postoperative Visit:**

- Mean LogMAR monocular BCDVA, mean binocular UCDVA, UCIVA, UCNVA, BCDVA, and contrast acuity will be reported for study group eyes and control group eyes at 3 months postoperative. Better visual acuity outcomes (lower mean LogMAR scores) for study group eyes are expected compared to control group eyes. Summary statistics (mean, standard deviation, median, minimum and maximum) will be reported for MRSE at 3 months postoperative for study group eyes and control group eyes. The difference between MRSE at 3 months postoperative visit and the target MRSE will be calculated. The difference is expected to be smaller (closer to zero) for study group eyes than that for control group eyes. Contrast acuity in the Study group at 3 months postoperative will be compared to the Control group.
- Mean change in total Standard Patient Evaluation of Eye Dryness (SPEED) score from Baseline visit to 3 months postoperative in the Study group will be compared to the Control group.

The SPEED score is the sum of frequency and severity scores with a range from 0 to 28. A lower SPEED score represents less frequent and/or less severe symptoms. The mean SPEED score will be reported at Baseline and 3 months postoperative visit. Greater mean change in SPEED score from Baseline to 3 months for study group eyes is expected.

- Mean change in total meibomian gland score in the Study group will be compared to the Control group from Baseline to 3 months postoperative. Greater mean change in total Meibomian gland score from Baseline to 3 months is expected for study group eyes than that for control group eyes.

- **Control Group 4-Month Postoperative Visit:**

- Mean change in LogMAR monocular BCDVA and UCDVA and mean change in LogMAR binocular UCDVA, UCIVA, UCNVA, BCDVA, and contrast acuity will be reported for control group eyes from 3 months to 4 months postoperative. Better visual acuity outcomes (lower mean LogMAR scores) at 4 months visit are expected.

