#### 4.2.2 ENDPOINTS EVALUATED AT 3-MONTH POSTOPERATIVELY

Mean LogMAR monocular BCDVA, mean LogMAR binocular UCDVA, UCIVA, UCNVA, BCDVA and contrast acuity will be reported for study group eyes/subjects and control group eyes/subjects at 3 months postoperatively. Better visual acuity outcomes (lower mean LogMAR scores) for study group eyes are expected compared to control group eyes.

Summary statistics (mean, standard deviation, median, minimum and maximum) will be reported for MRSE at 3 months postoperative visit for study group eyes and control group eyes. The difference between MRSE at 3 months postoperative visit and the target MRSE will be calculated. The difference is expected to be smaller (closer to zero) for study group eyes than that for control group eyes.

Mean change in total Standard Patient Evaluation of Eye Dryness (SPEED) score from Baseline visit to 3 months postoperative in the study group subjects will be compared to the control group subjects. The SPEED score is the sum of frequency and severity scores with a range from 0 to 28. A lower SPEED score represents less frequent and/or less severe dry eye symptoms. The mean SPEED score will be reported at Baseline and 3 months postoperative visit. Greater mean change in SPEED score from Baseline to 3 months for study group subjects is expected.

Mean change in total Meibomian gland score from Baseline visit in the study group eyes will be compared to the control group eyes. Greater mean change in total Meibomian gland score is expected for study group eyes than that for control group eyes.

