### 4.2.3 ENDPOINTS EVALUATED AT 4-MONTH POSTOPERATIVE FOR CONTROL GROUP SUBJECTS ONLY

Mean change in LogMAR monocular BCDVA and UCDVA and mean change in LogMAR binocular UCDVA, UCIVA, UCNVA, BCDVA and contrast acuity will be reported for control group eyes from 3 months to 4 months postoperative visit. Better visual acuity outcomes (lower mean LogMAR scores) at 4 months visit are expected.

Mean MRSE at 4 months postoperative will be compared to target MRSE. Frequency and percent of eyes with MRSE within 0.50 D and within 1.00 D of target MRSE at 4 months postoperative will be reported.

Version 1.0 5 SAP/DRYE-102-SELF

Mean change in total Meibomian gland score and mean change in total SPEED score from 3 months to 4 months postoperative will be reported. An increase in both mean total Meibomian gland score and mean total SPEED are expected.

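### SAP Appendix I lists SPEED by eye and measures the month-4 SPEED and gland-score changes from the wrong visit; both documents also expect SPEED to rise after treatment

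*SAP*

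**What the plan says.** **Unit.** Protocol Appendix K describes one questionnaire, completed by the subject, that gives one total. SAP 4.2.2 treats it that way: "Greater mean change in SPEED score from Baseline to 3 months for study group subjects is expected". Protocol 20.3 has the same sentence with a different unit: "Greater mean change in SPEED score from Baseline to 3 months for study group eyes is expected". SAP Appendix I gives the unit as eyes for the baseline row ("SPEED score at 1 st preop visit (baseline") and the 3-month row ("Mean change in SPEED score from baseline- (N, Mean, SD, Min, Max, 95% CI"), and as Control group eyes only for the 4-month row.

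**Reference visit.** For the Control group at month 4, SAP 4.2.3 says that "mean change in total SPEED score from 3 months to 4 months postoperative will be reported", and treats the total meibomian gland score the same way. Protocol 6.2 and 20.3 agree. The two month-4 rows of Appendix I for these measures instead take change from baseline, which Appendix I identifies as the first preoperative visit. A neighbouring row in the same block reads "Contrast acuity at 4M and change from 3M to 4M".

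**Direction.** SAP 4.2.2 states that "A lower SPEED score represents less frequent and/or less severe dry eye symptoms". SAP 4.2.3 then says of the period after crossover treatment: "An increase in both mean total Meibomian gland score and mean total SPEED are expected". Protocol 20.3 states the same expectation.

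**The concern.** SPEED is not a key endpoint. It is, however, the instrument that Protocol Appendices D and K name for evaluating ocular comfort, and ocular comfort is part of the study objective. Appendix I is the list from which the tables will be programmed.

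- Tabulating a subject-level score by eye counts each subject twice. The N is inflated and the confidence intervals are too narrow.
- With change from baseline at month 4, no listed table shows the prespecified crossover change in SPEED or gland score. The listed change also covers cataract surgery and the untreated postoperative months.
- An expected rise in SPEED means that symptoms are predicted to worsen after treatment. Protocol 17 expects LipiFlow to improve dry eye symptoms. The 3-month text does not settle the sign, because it speaks only of a greater mean change.

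**Working it through.** **1. SPEED is one score per subject.** Appendix K scores four symptom groups, each with frequency 0 to 3 and severity 0 to 4. The maximum is 4 × (3 + 4) = 28, which is the stated top of the range, so there is no separate total for each eye. Appendix I does separate units elsewhere: binocular acuity, contrast acuity and bothersome symptoms are listed by subjects. Listing SPEED by eyes is therefore not a general convention of the table.

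**2. Effect of tabulating by eye.** Inputs: 55 evaluable subjects per arm (SAP 1). Assumption: two eyes per subject, with the SPEED total entered once for each eye.

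- N per arm: 2 × 55 = 110, from 55 distinct values. The mean does not change.
- With S the sum of squares of the 55 values, the correct squared SE is S/(54 × 55). The duplicated one is 2S/(109 × 110).
- SE ratio = √[2 × 54 × 55 / (109 × 110)] = √(5940/11990) = 0.704.
- 95% CI half-width ratio = 0.704 × t(0.975; 109) / t(0.975; 54) = 0.7039 × 1.982/2.005 = 0.696, so the interval is about 30% too narrow.
- Coverage = P(|t with 54 df| < 0.7039 × 1.982 = 1.395) = 0.831.

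Protocol 10.6 Note 3 allows some subjects to contribute one eye. The documents give no rate, so three values were assumed and simulated (400,000 normal samples each):

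| One-eye subjects of 55 (assumed) | N listed | Half-width ratio | Coverage |
|---|---|---|---|
| 0 (exact) | 110 | 0.696 | 83.1% |
| 3 | 107 | 0.706 | 83.5% |
| 6 | 104 | 0.716 | 83.7% |
| 11 | 99 | 0.734 | 84.4% |

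The result barely depends on this assumption. The SAP names no test for SPEED, so no type I error figure is attached.

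**3. What the month-4 change covers.** Visit windows for the Control group (Protocol 10.2):

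- Visit #1 to Visit #2: 2 to 4 weeks.
- Second-eye surgery to month 3: 10 to 14 weeks.
- Month 3 to crossover treatment: 0 to 1 week.
- Crossover treatment to month 4: 4 to 6 weeks.

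| Interval | Length | Share after crossover treatment |
|---|---|---|
| Baseline to month 4 (Appendix I) | at least 2 + 10 + 0 + 4 = 16 weeks, plus time for surgery | at most 6/(2 + 10 + 0 + 6) = 6/18 = 1/3 |
| Month 3 to month 4 (SAP 4.2.3) | 0 + 4 = 4 to 1 + 6 = 7 weeks | at least 4/(1 + 4) = 4/5 |

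Protocol Appendix B collects both measures at 3 and 4 months, so the prespecified change can be computed from planned data.

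**4. Direction.** On a 0 to 28 scale where lower is better, an improvement is a negative change. An expected increase contradicts the scale definition in both documents and Protocol 17. For the gland score, where higher is better, an increase is the right expectation. The sentence joins two scales that run in opposite directions.

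**The case against.** The SAP body is already right on the first two points: 4.2.2 compares subjects, and 4.2.3 requires the 3-to-4-month change to be reported. Appendix I is a table listing and does not define the endpoints. A programmer may enter each SPEED total once whatever the unit column says, and nothing instructs anyone to copy it to both eyes. The direction sentence is only an expectation: no test, success criterion or decision rests on it, and the computed change would be the same. In the 3-month row, change from baseline is correct and only the unit is wrong.

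Much of this stands. The precision figures are conditional on tabulation by eye, the direction error is a wording correction, and the 3-month reference visit needs no change. It does not remove the point. No rule says that the SAP body overrides Appendix I. Protocol 20.3 itself uses eyes for SPEED, and the direction error is in the body text of both documents. A listing that asks for a different change from the one defined in the text leaves the choice to whoever programs it.

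**Conclusion.** The point holds in all three parts. The most important is the month-4 reference visit, because following Appendix I would report a different quantity from the prespecified one for both SPEED and gland score. Next is the unit: tabulated by eye, SPEED would show an N of 110 instead of 55 per arm, and its nominal 95% intervals would cover about 83% (83% to 84% if up to a fifth of subjects contribute one eye). This assumes each subject's total is repeated for each eye. The direction wording is wrong but has no numerical consequence. These are other endpoints with no named test; the monocular UCDVA endpoint and the sample size are not affected.

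**What to change.** - **SAP Appendix I, unit:** set the three SPEED rows (baseline, 3 months, 4 months) to subjects, with Control group subjects only at month 4. Keep the gland score by eyes, since it is graded per eye.
- **SAP Appendix I, reference visit:** change the two month-4 rows for SPEED and total gland score to mean change from 3M to 4M, matching the acuity and contrast rows.
- **SAP 4.2.3 and Protocol 20.3 (4 months):** state that mean gland score is expected to increase and mean SPEED to decrease.
- **SAP 4.2.2 and Protocol 20.3 (3 months):** state that a greater mean reduction in SPEED is expected in study group subjects. In the protocol this also replaces eyes with subjects.
- **Optional:** note that the 3-to-4-month change is an uncontrolled within-group comparison.

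The cost is a few words in each place. No data collection or study procedure changes.
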